3.4 SELECTION OF STUDY POPULATION

3.4.1 Inclusion Criteria Part 1

Eligible subjects will be considered for inclusion in this study if they meet **all** of the following criteria:

- 1. Men and women ≥18 years of age.
- 2. Relapsed/Refractory Cohort: A confirmed diagnosis of FL Grade 1, 2, or 3a that has relapsed after, or been refractory to ≥1 prior therapy for FL and which requires treatment per National Cancer Institute or International Working Group guidelines. Documented failure to achieve at least PR with, or documented disease progression after, the most recent treatment regimen.
 - Treatment-naive Cohort: A confirmed diagnosis of FL Grade 1, 2, or 3a that requires treatment per National Cancer Institute or International Working Group guidelines in subjects who have not previously received systemic anticancer therapy for FL.
- 3. Presence of radiographically measurable lymphadenopathy or extranodal lymphoid malignancy (defined as the presence of ≥1 lesion that measures ≥2.0 cm in the longest dimension and ≥1.0 cm in the longest perpendicular dimension as assessed by computed tomography [CT] scan).
- 4. ECOG performance status of ≤2.
- 5. Agreement of women of childbearing potential (WOCBP) to use highly effective methods of contraception during the study and for 2 days after the last dose of acalabrutinib or 3 months after the last dose of rituximab, whichever is longer, if sexually active and able to bear or beget children. Highly effective forms of contraception are defined in Section 3.7.6.
- 6. Men must agree to refrain from sperm donation during the study and for 3 months after the last dose of rituximab.
- 7. Willing and able to participate in all required evaluations and procedures in this study protocol including swallowing capsules or tablets without difficulty.
- 8. Ability to understand the purpose and risks of the study and provide signed and dated informed consent and authorization to use protected health information (in accordance with national and local patient privacy regulations).

3.4.2 Exclusion Criteria Part 1

Subjects will be ineligible for this study if they meet **any** of the following criteria:

 Prior malignancy (other than indolent B-cell NHL), except for adequately treated basal cell or squamous cell skin cancer, in situ cancer, or other cancer from which the subject has been disease free for ≥2 years.

- 2. Known CNS lymphoma or leptomeningeal disease.
- 3. A life-threatening illness, medical condition, or organ system dysfunction which, in the investigator's opinion, could compromise the subject's safety, interfere with the absorption or metabolism of acalabrutinib, or put the study outcomes at undue risk.
- 4. Known history of a bleeding diathesis (e.g., hemophilia, von Willebrand disease).
- Significant cardiovascular disease such as uncontrolled or symptomatic arrhythmias, congestive heart failure, or myocardial infarction within 6 months of screening, or any Class 3 or 4 cardiac disease as defined by the New York Heart Association Functional Classification, or corrected QT interval (QTc) >480 msec.
- Malabsorption syndrome, disease significantly affecting gastrointestinal function, or resection of the stomach or small bowel, gastric bypass, symptomatic inflammatory bowel disease, or partial or complete bowel obstruction.
- 7. Any immunotherapy within 4 weeks of first dose of study drug.
- 8. Relapsed/Refractory Cohort: The time from the last dose of the most recent chemotherapy or experimental therapy to the first dose of study drug is <5 times the half-life of the previously administered agent(s).
- 9. Prior exposure to a BCR inhibitor (e.g., BTK, phosphonositide-3 kinase [PI3K], or spleen tyrosine kinase [SYK] inhibitors) or BCL-2 inhibitor (e.g., venetoclax).
- Known history of anaphylaxis or hypersensitivity to rituximab (Rituxan/MabThera) or any of its components.
- 11. Ongoing immunosuppressive therapy, including systemic or enteric corticosteroids for treatment of FL or other conditions. Note: Subjects may use topical or inhaled corticosteroids or low-dose steroids (≤20 mg of prednisone or equivalent) as therapy for comorbid conditions. During study participation, subjects may also receive systemic or enteric corticosteroids as needed for treatment-emergent comorbid conditions.
- 12. Grade ≥2 toxicity (other than alopecia) continuing from prior anticancer therapy including radiation.
- 13. Known history of HIV or active infection with hepatitis C virus (HCV) or any uncontrolled active systemic infection.

- 14. Known hepatitis B infection or positive for hepatitis B surface antigen (HBsAg) or hepatitis B core antibody (anti-HBc). Since intravenous immunoglobulins (IVIG) may cause false positive hepatitis serology, subjects who are receiving prophylactic IVIG and have positive HBsAg or anti-HBc must have negative hepatitis B DNA to be eligible.
- 15. Major surgery within 4 weeks before first dose of acalabrutinib.
- 16. Uncontrolled autoimmune hemolytic anemia or idiopathic thrombocytopenia purpura.
- 17. History of stroke or intracranial hemorrhage within 6 months before the first dose of acalabrutinib.
- 18. Requires or receiving anticoagulation with warfarin or equivalent vitamin K antagonist (e.g., phenprocoumon) within 7 days of first dose of study drug.
- 19. Requires treatment with proton-pump inhibitors (e.g., omeprazole, esomeprazole, lansoprazole, dexlansoprazole, rabeprazole, or pantoprazole). Note: this criterion no longer applies to subjects who have switched from acalabrutinib capsules to tablets.
- 20. Received a live virus vaccination within 28 days of first dose of study drug.
- 21. ANC <0.75 \times 10⁹/L or platelet count <50 \times 10⁹/L. For subjects with documented disease involvement in the bone marrow, ANC <0.50 \times 10⁹/L or platelet count <30 \times 10⁹/L.
- 22. Creatinine >2.5 × institutional upper limit of normal (ULN); total bilirubin >2.5 × ULN; and aspartate aminotransferase (AST) or alanine aminotransferase (ALT) >3.0 × ULN.
- 23. Breastfeeding or pregnant.
- 24. Concurrent participation in another therapeutic clinical trial.
- 25. Presence of a gastrointestinal ulcer diagnosed by endoscopy within 3 months before screening.

3.4.3 Inclusion Criteria Part 2

Eligible subjects will be considered for inclusion in this study if they meet **all** of the following criteria:

- 1. Men and women ≥18 years of age.
- 2. Histologically confirmed MZL including splenic, nodal, and extranodal sub-types
 - Subjects with splenic MZL must have an additional measurable lesion, nodal or extranodal, as described in inclusion criterion #4;

b. Subjects with gastric MALT lymphoma must be H. pylori-negative (including subjects after successful elimination of H. pylori) or refractory to H. pylori-eradication therapy by a minimum time of 12 months by a pathology confirmation or by a ¹³C urea test (proton-pump inhibitors and H2 blockers should be discontinued or withheld for at least 14 days and 7 days, respectively, and antibiotics for treating H. pylori, such as those with anti-helicobacter action and bismuth preparations, should be withdrawn at least 30 days before H. pylori testing [Savarino et al. 1999]).

3. Previous therapy:

- a. Cohort 1: Previously received 1 or more lines of systemic therapy including at least 1 CD20-directed regimen (either as monotherapy or as chemoimmunotherapy for MZL) with documented failure to achieve at least PR, or documented disease progression after the most recent treatment regimen.
- b. Cohort 2: Previously received 1 or more lines of therapy including at least 1 prior systemic therapy for MZL or radiation therapy with documented failure to achieve at least PR, or document disease progression after the most recent treatment regimen.
- 4. Presence of radiographically measurable lymphadenopathy or extranodal lymphoid malignancy (defined as the presence of ≥1 lesion that measures ≥2.0 cm in the longest dimension and ≥1.0 cm in the longest perpendicular dimension as assessed by CT scan). Lesions in anatomical locations, such as extremities or soft tissue lesions, that are not well visualized by CT may be measured by magnetic resonance imaging (MRI) instead; subjects with spleen-only disease are considered as not having measurable disease.
- 5. ECOG performance status of ≤2.
- 6. WOCBP must agree to use highly effective methods of contraception during the study and for 2 days after the last dose of acalabrutinib or 12 months after the last dose of rituximab, whichever is longer, if sexually active and able to bear or beget children. Highly effective methods of contraception are defined in Section 3.7.6.
- 7. Men must agree to refrain from sperm donation during the study and for 3 months after the last dose of rituximab.
- 8. Willing and able to participate in all required evaluations and procedures in this study protocol including swallowing capsules or tablets without difficulty.
- 9. Ability to understand the purpose and risks of the study and provide signed and

dated informed consent and authorization to use protected health information (in accordance with national patient privacy regulations).

3.4.4 Exclusion Criteria Part 2

Subjects will be ineligible for this study if they meet **any** of the following criteria:

- Prior malignancy (other than indolent B-cell NHL), except for adequately treated basal cell or squamous cell skin cancer, in situ cancer, or other cancer from which the subject has been disease free for ≥2 years.
- 2. Known medically apparent CNS lymphoma or leptomeningeal disease.
- 3. Known evidence of transformation to another aggressive lymphoma.
- 4. A life-threatening illness, medical condition, or organ system dysfunction which, in the investigator's opinion, could compromise the subject's safety, interfere with the absorption or metabolism of acalabrutinib, or put the study outcomes at undue risk.
- 5. Known history of a bleeding diathesis (e.g., hemophilia, von Willebrand disease).
- 6. Significant cardiovascular disease such as uncontrolled or symptomatic arrhythmias, congestive heart failure, or myocardial infarction within 6 months of screening, or any Class 3 or 4 cardiac disease as defined by the New York Heart Association Functional Classification, or corrected QT interval using Fridericia formula (QTcF) >480 msec.
- 7. Malabsorption syndrome, disease significantly affecting gastrointestinal function (excluding gastric MALT), or resection of the stomach or small bowel, gastric bypass, symptomatic inflammatory bowel disease, or partial or complete bowel obstruction.
- 8. This criterion was removed under Amendment 5.
- 9. This criterion was removed under Amendment 5.
- 10. Prior exposure to a BCR inhibitor (e.g., BTK, or SYK inhibitors).
- 11. For Cohort 2, evidence of CD20⁻ MZL and/or known history of anaphylaxis or hypersensitivity to rituximab (Rituxan/MabThera) or any of its components.
- 12. Ongoing immunosuppressive therapy, including systemic or enteric corticosteroids for treatment or other conditions within 1 week before the first dose of study drug. Note: Subjects may use topical or inhaled corticosteroids or low-dose steroids (≤20 mg of prednisone or equivalent for up to 2 weeks) as therapy for comorbid conditions. However, subjects requiring systemic steroids at daily doses >20 mg prednisone equivalent of systemic exposure are not allowed.
- 13. Grade ≥2 toxicity (other than alopecia or laboratory value requirements mentioned in

Part 2) continuing from prior anticancer therapy including radiation.

- 14. Uncontrolled active systemic fungal, bacterial, viral, or other infection (defined as exhibiting ongoing signs/symptoms related to the infection and without improvement, despite appropriate antibiotics or other treatment), or intravenous anti-infective treatment within 2 weeks before first dose of study drug.
- 15. Known history of infection with HIV.
- 16. Serologic status reflecting active hepatitis B or C infection.
 - a. Subjects who are anti-HBc positive and who are surface antigen negative will need to have a negative hepatitis B virus (HBV) DNA polymerase chain reaction (PCR) result before enrollment. Subjects who are HBsAg positive or hepatitis B PCR positive will be excluded.
 - Subjects who are anti-HCV positive will need to have a negative PCR result before enrollment. Subjects who are hepatitis C PCR positive will be excluded.
- 17. History of allogeneic stem cell (or organ) transplantation.
- 18. This criterion was removed under Amendment 5.
- 19. Major surgery within 4 weeks before first dose of acalabrutinib.
- 20. Uncontrolled autoimmune hemolytic anemia or idiopathic thrombocytopenia purpura.
- 21. History of stroke or intracranial hemorrhage within 6 months before the first dose of acalabrutinib.
- 22. Requires or receiving anticoagulation with warfarin or equivalent vitamin K antagonist (e.g., phenprocoumon) within 7 days of first dose of study drug.
- 23. Requires treatment with proton-pump inhibitors (e.g., omeprazole, esomeprazole, lansoprazole, dexlansoprazole, rabeprazole, or pantoprazole). Note: this criterion no longer applies to subjects who have switched from acalabrutinib capsules to tablets.
- 24. Received a live virus vaccination within 28 days of first dose of study drug.
- 25. ANC <1.0 × 10^9 /L or platelet count <100 × 10^9 /L. For subjects with documented disease involvement in the bone marrow, ANC <0.50 × 10^9 /L or platelet count <30 × 10^9 /L.
- 26. Creatinine >1.5 × institutional ULN; total bilirubin >1.5 × ULN; and AST or ALT >2.5 × ULN.
- 27. Breastfeeding or pregnant.
- 28. Concurrent participation in another therapeutic clinical trial.

29. In the absence of gastric MALT (subject to inclusion criterion 2b) presence of a gastrointestinal ulcer diagnosed by endoscopy within 3 months before screening or diagnosed >3 months before screening and without confirmed resolution by endoscopy.

- 30. Received any chemotherapy, external beam radiation therapy, anticancer antibodies, or investigational drug within 30 days before first dose of study drug.
- 31. History of or ongoing progressive multifocal leukoencephalopathy (PML).

3.4.5 Inclusion Criteria Part 3

Eligible subjects will be considered for inclusion in this study if they meet **all** of the following criteria.

- 1. Men and women ≥18 years of age.
- For subjects with FL: Pathologically confirmed diagnosis of FL Grade 1, 2, or 3a that
 has relapsed after, or been refractory to, ≥1 prior therapy for FL and which requires
 treatment per National Cancer Institute or European Society for Medical Oncology
 (ESMO) clinical practice guidelines.
- 3. This criterion was removed under Amendment 6.
- 4. Subjects must have previously received at least 1 frontline standard chemoimmunotherapy regimen.
- 5. Subjects with suspected residual disease after the treatment regimen directly preceding study enrollment must have biopsy-demonstrated residual FL.
- Documented R/R disease, defined as either: 1) recurrence of disease after a CR or PR, or 2) stable disease or progressive disease at completion of the treatment regimen preceding entry to the study (residual disease).
- 7. Presence of radiographically measurable lymphadenopathy or extranodal lymphoid malignancy (defined as the presence of ≥1 lesion that measures ≥2.0 cm in the longest dimension and ≥1.0 cm in the longest perpendicular dimension as assessed by CT scan).
- 8. ECOG performance status of ≤2.
- 9. Females of reproductive potential must
 - a. have 2 negative pregnancy tests prior to initiating treatment with lenalidomide. The first should be within 10 to 14 days and the second test within 24 hours prior to first dose of lenalidomide.
 - b. commit to abstain continuously from heterosexual sex or use highly effective

methods of contraception. Contraception must be used beginning 4 weeks prior to initiating treatment with lenalidomide, during therapy with any study drug, and during dose interruptions for lenalidomide. Contraception must be used for 2 days after the last dose of acalabrutinib,12 months after the last dose of rituximab, or 4 weeks after the last dose of lenalidomide, whichever is later.

- 10. Men must agree to use a synthetic or latex condom during any sexual contact with female of reproductive potential or with a pregnant partner while taking lenalidomide and for up to 4 weeks after last dose of lenalidomide, even if they have undergone a successful vasectomy since lenalidomide is present in the semen. Men must agree to refrain from sperm donation during the study and for 3 months after the last dose of rituximab or 4 weeks after the last dose of lenalidomide, whichever is later.
- 11. Subjects must not donate blood during treatment with lenalidomide and for 4 weeks after discontinuation of lenalidomide.
- 12. Willing and able to participate in all required evaluations and procedures in this study protocol including swallowing capsules or tablets without difficulty.
- 13. Ability to understand the purpose and risks of the study and provide signed and dated informed consent and authorization to use protected health information (in accordance with national patient privacy regulations).

3.4.6 Exclusion Criteria Part 3

- Prior malignancy, except for adequately treated basal cell or squamous cell skin cancer, in situ cancer, or other cancer from which the subject has been disease free for ≥2 years.
- Subjects for whom the goal of therapy is tumor debulking before stem cell transplant.
- 3. Known history or presence of CNS lymphoma or leptomeningeal disease.
- Transformed DLBCL or DLBCL with coexistent histologies (e.g., FL or mucosa-associated lymphoid tissue and primary mediastinal large B-cell lymphoma [PMBCL]).
- 5. A life-threatening illness, medical condition, or organ system dysfunction that, in the investigator's opinion, could compromise the subject's safety, interfere with the absorption or metabolism of acalabrutinib or lenalidomide, or put the study outcomes at undue risk.
- 6. Known history of a bleeding diathesis (e.g., hemophilia, von Willebrand disease).
- 7. Significant cardiovascular disease such as uncontrolled or symptomatic arrhythmias, congestive heart failure, or myocardial infarction within 6 months of screening, or any

Class 3 or 4 cardiac disease as defined by the New York Heart Association Functional Classification, or QTcF >480 msec. Exception: Subjects with controlled, asymptomatic atrial fibrillation during screening are allowed to be enrolled on study.

- 8. Malabsorption syndrome, disease significantly affecting gastrointestinal function, or resection of the stomach or small bowel, gastric bypass, symptomatic inflammatory bowel disease, or partial or complete bowel obstruction.
- 9. Received any chemotherapy, external beam radiation therapy, anticancer antibodies, or investigational drug within 30 days before first dose of study drug.
- 10. Prior exposure to a BCR inhibitor (e.g., BTK or SYK inhibitors), lenalidomide, or CAR-T cell therapy.
- 11. Known history of anaphylaxis or hypersensitivity to rituximab (Rituxan/MabThera) or any of its components.
- 12. Subjects with a prior history of Grade 4 rash associated with thalidomide treatment.
- 13. Ongoing immunosuppressive therapy, including systemic (e.g., IV or oral) corticosteroids within 2 weeks before the first dose of study drug. Note: Subjects may use topical or inhaled corticosteroids or low-dose steroids (≤20 mg prednisone equivalent/day for ≤2 weeks) as a therapy for comorbid conditions. During study participation, subjects may also receive systemic (e.g., IV or oral) corticosteroids as needed for treatment-emergent comorbid conditions.
- 14. Grade ≥2 toxicity (other than alopecia or laboratory value requirements mentioned in Part 3 exclusion criteria) continuing from prior anticancer therapy including radiation.
- 15. Uncontrolled active systemic fungal, bacterial, viral, or other infection (defined as exhibiting ongoing signs or symptoms related to the infection and without improvement, despite appropriate antibiotics or other treatment), or intravenous anti-infective treatment within 2 weeks before first dose of study drug.
- 16. Known history of infection with HIV.
- 17. Serologic status reflecting active hepatitis B or C infection.
 - a. Subjects who are anti-HBc positive and who are surface antigen negative will need to have a negative PCR result before enrollment. Subjects who are HBsAg positive or hepatitis B PCR positive will be excluded.
 - Subjects who are HCV antibody (anti-HCV) positive will need to have a negative PCR result before enrollment. Subjects who are HCV PCR positive will be excluded.
- 18. History of allogeneic stem cell (or organ) transplantation.

- 19. Major surgery within 4 weeks before first dose of acalabrutinib.
- 20. Uncontrolled autoimmune hemolytic anemia or idiopathic thrombocytopenia purpura.
- 21. History of stroke or intracranial hemorrhage within 6 months before the first dose of acalabrutinib.
- 22. Requires or has received anticoagulation with warfarin or equivalent vitamin K antagonist (e.g., phenprocoumon) within 7 days of first dose of study drug.
- 23. Received a live virus vaccination within 28 days of first dose of study drug.
- 24. ANC <1.0 × 10⁹/L or platelet count <75 × 10⁹/L. Subjects will only be considered eligible if peripheral blood counts can be maintained independent of growth factors or transfusions during screening.
- 25. Creatinine clearance of <60 mL/min, calculated using the formula of Cockcroft and Gault [(140-Age) * Mass (kg)/(72 * creatinine mg/dL) * 0.85 if female].
- 26. Total bilirubin >1.5 × ULN, or AST or ALT >2.5 × ULN, unless directly attributable to Gilbert's syndrome.
- 27. Requires treatment with a strong CYP3a inhibitor/inducer.
- 28. Requires treatment with proton-pump inhibitors (e.g., omeprazole, esomeprazole, lansoprazole, dexlansoprazole, rabeprazole or pantoprazole). Subject receiving proton-pump inhibitors who switch to H2-receptor antagonists or antacids are eligible for enrollment to this study. Note: this criterion no longer applies to subjects who have switched from acalabrutinib capsules to tablets.
- 29. Breastfeeding or pregnant.
- 30. Concurrent participation in another therapeutic clinical trial.
- 31. History of or ongoing PML.

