	A total of approximately 26 to 32 subjects are to be enrolled in Part 3.
Inclusion Criteria:	Eligible subjects will be considered for inclusion in this study if they meet all of the following criteria.
	Part 1 1. Men and women ≥18 years of age.

- 2. Relapsed/Refractory Cohort: A confirmed diagnosis of FL Grade 1, 2, or 3a that has relapsed after, or been refractory to ≥1 prior therapy for FL and which requires treatment per National Cancer Institute or International Working Group guidelines. Documented failure to achieve at least partial remission (PR) with, or documented disease progression after, the most recent treatment regimen.
 Treatment-Naive Cohort: A confirmed diagnosis of FL Grade 1, 2, or 3a that requires treatment per National Cancer Institute or International Working Group guidelines in subjects who have not previously received systemic anticancer therapy for FL.
- 3. Presence of radiographically measurable lymphadenopathy or extranodal lymphoid malignancy (defined as the presence of ≥1 lesion that measures ≥2.0 cm in the longest dimension and ≥1.0 cm in the longest perpendicular dimension as assessed by computed tomography [CT] scan).
- 4. Eastern Cooperative Oncology Group (ECOG) performance status of ≤2.
- 5. Agreement to use highly effective methods of contraception during the study and for 2 days after the last dose of acalabrutinib or 12 months after the last dose of rituximab, whichever is longer, if sexually active and able to bear or beget children. Highly effective forms of contraception are defined in the protocol.
- 6. Men must agree to refrain from sperm donation during the study and for 3 months after the last dose of rituximab.
- 7. Willing and able to participate in all required evaluations and procedures in this study protocol including swallowing capsules or tablets without difficulty.
- Ability to understand the purpose and risks of the study and provide signed and dated informed consent and authorization to use protected health information (in accordance with national and local patient privacy regulations).

Part 2

- 1. Men and women ≥18 years of age.
- 2. Histologically confirmed MZL including splenic, nodal, and extranodal sub-types
 - Subjects with splenic MZL must have an additional measurable lesion, nodal or extranodal, as described in inclusion criterion #4:

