Hormonal contraception may be susceptible to interaction with study or other drugs, which may reduce the efficacy of the contraception method.

†Abstinence (relative to heterosexual activity) can only be used as the sole method of contraception if it is consistently employed as the subject's preferred and usual lifestyle and if considered acceptable by local regulatory agencies and Institutional Review Boards (IRBs)/Independent Ethics Committees (IECs). Periodic abstinence (e.g., calendar, ovulation, sympto-thermal, and postovulation methods) and withdrawal (coitus interruptus), spermicides only, and lactational amenorrhea method are not acceptable methods of contraception.

‡If a contraceptive method listed above is restricted by local regulations/guidelines, then it does not qualify as an acceptable method of contraception for subjects participating at sites in this country/region.

Results of definitive reproductive toxicity studies with acalabrutinib are provided in the current Acalabrutinib Investigator Brochure.

Women of childbearing potential (see definition of WOCBP potential above) who are sexually active must agree to use highly effective forms of contraception during the study and 2 days after the last dose of acalabrutinib, 12 months after the last dose of rituximab, or 4 weeks after the last dose of lenalidomide, whichever is longer.

Male subjects who are sexually active with a WOCBP partner or a pregnant partner must use a condom during treatment and until 4 weeks after the last dose of lenalidomide or 3 months after the last dose of rituximab. Men must also refrain from donating sperm during the study for 3 months after the last dose of rituximab, or 4 weeks after the last dose of lenalidomide, whichever is longer.

Subjects should be informed that taking the study medication may involve unknown risks to the fetus (unborn baby) if pregnancy were to occur during the study. To participate in the study subjects of childbearing potential must adhere to the contraception

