requirement (described above) from the day of study medication initiation (or 14 days prior to the initiation of study medication for oral contraception) throughout the study period up to 2 days after the last dose of acalabrutinib (for WOCBP only), 12 months after the last dose of rituximab, or 4 weeks after the last dose of lenalidomide, whichever is longer. If there is any question that a subject of childbearing potential will not reliably comply with the requirements for contraception, that subject should not be entered into the study.

Subjects should promptly notify the investigator if they, or their partners, become pregnant during this period. If a female subject becomes pregnant during the treatment period, she must discontinue study drug immediately. Pregnancy in a female subject or a male subject's partner must be reported as outlined in Section 6.3.4.

Blood Donation

Subjects must not donate blood during treatment with lenalidomide and for 4 weeks after discontinuation of lenalidomide because the bloods might be given to a pregnant female patient whose fetus must not be exposed to lenalidomide.

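### Contraception windows differ between the synopsis, the eligibility criteria and Section 3.7.6 and need reconciling, above all the condom rule for Part 3 men

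*Protocol*

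**What the plan says.** **Men, Part 3.** Inclusion criterion 10 (Section 3.4.5, repeated in the synopsis) requires condoms while lenalidomide is being taken "and for up to 4 weeks after last dose of lenalidomide, even if they have undergone a" vasectomy. It does not link condoms to rituximab. Section 3.7.6 says that a sexually active man with a pregnant partner or a partner of childbearing potential "must use a condom during treatment and until 4 weeks after the last dose of lenalidomide or 3 months after the last dose of rituximab". It gives no rule for choosing between the two limbs, although its next sentence, on sperm donation, does give one.

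**Women, Part 1.** Criterion 5 in Section 3.4.1 sets the period at 2 days after acalabrutinib "or 3 months after the last dose of rituximab, whichever is longer". The synopsis copy of criterion 5 says "or 12 months after the last dose of rituximab, whichever is longer". Section 3.7.6, to which criterion 5 refers for acceptable methods, says "12 months after the last dose of rituximab, or 4 weeks after the last dose of lenalidomide, whichever is longer".

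**Women, Part 3, start.** Criterion 9b (Section 3.4.5 and synopsis) says: "Contraception must be used beginning 4 weeks prior to initiating treatment with lenalidomide". Section 3.7.6 counts "from the day of study medication initiation", or from 14 days before it for oral contraception. That paragraph names lenalidomide when it defines the end of the window, so it covers Part 3, but its start rule makes no exception for lenalidomide.

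**The concern.** These are instructions to subjects about fetal exposure. Section 3.7.3 records a boxed warning of birth defects and embryo-fetal death for lenalidomide, and Section 3.7.2 lists embryo-fetal toxicity for rituximab. The protocol has no rule on whether the eligibility criteria or Section 3.7.6 prevails, so two sites could each follow it and still tell similar subjects different things. The lenalidomide REMS programme is not a complete backstop: Appendix 12 records that subjects in Canada are not required to take part.

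The male rule matters longest, because in Part 3 rituximab maintenance continues well after lenalidomide stops. What is at stake is subject protection and consistent conduct. No endpoint, analysis population, estimate or dose-limiting-toxicity decision depends on it.

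**Working it through.** The plan gives no figure to reproduce. The check is a comparison of texts plus calendar arithmetic on 28-day cycles, with Cycle 1 Day 1 as day 1.

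**1. Men, Part 3**

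Inputs:
- Lenalidomide is given on Days 1 to 21 for up to 12 cycles (Section 3.3).
- Rituximab ends at Cycle 26 (Section 3.1), on Day 1 of the cycle.
- Three months is taken as 91 days (assumption).

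Steps:
- Last planned lenalidomide dose, Cycle 12 Day 21: 11 × 28 + 21 = day 329.
- Last planned rituximab dose, Cycle 26 Day 1: 25 × 28 + 1 = day 701.
- Condom use ends under criterion 10: 329 + 28 = day 357.
- Condom use ends under the rituximab limb of Section 3.7.6: 701 + 91 = day 792.
- Difference: 792 − 357 = 435 days.

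This applies to a man who completes all planned lenalidomide and rituximab without delay. If rituximab stops earlier and lenalidomide is completed, the gap shrinks.

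**2. Women, Part 1**

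| Place | Months after last rituximab |
|---|---|
| Section 3.4.1, criterion 5 | 3 |
| Synopsis, criterion 5 | 12 |
| Section 3.7.6 | 12 |
| Section 6.3.4 (pregnancy reporting) | 12 |

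Difference: 12 − 3 = 9 months. The 3-month figure for women appears only in Section 3.4.1. Because the synopsis copy of the same criterion says 12, it does not read as a deliberate Part 1 rule.

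Could the difference still affect anyone?
- Part 1 enrolment was complete at Amendment 4 (Section 3.1), and Amendment 6 is dated 5 March 2020 (SAP Section 1).
- Allow the 21-day Part 1 screening window: first dose by about 26 March 2020.
- Last rituximab, Cycle 6 Day 1, is day 5 × 28 + 1 = 141, or 140 days later: about 13 August 2020.
- Twelve months on is about August 2021.
- The current text summarises an amendment dated 14 July 2022 (Appendix 12), about 11 months after that.

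Barring long dose delays, no Part 1 woman would still be inside the 12-month window.

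**3. Women, Part 3, start**

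- Criterion 9b: 28 days before lenalidomide.
- Section 3.7.6: 0 days before initiation, or 14 days for oral contraception.
- Difference: 28 − 0 = 28 days, or 28 − 14 = 14 days.

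A woman who meets criterion 9b also meets Section 3.7.6. The reverse does not hold.

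**The case against.** The strongest reply is that little of this is live and that none of it touches the analysis. Much of that stands.

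- **Part 1.** A reader might infer that Part 1 women are now exposed to a 9-month shortfall. The dates do not support this. Contraception is also required throughout the study, so the two figures could diverge only for a woman who left the study and stopped acalabrutinib within 12 months of her last rituximab dose.
- **Part 3 start.** A reader might call the two start times incompatible. They are nested: criterion 9b is the stricter, lenalidomide-specific entry condition, and a woman who does not commit to it cannot enrol. What remains is a general section that states a later start without pointing to the exception.
- **Part 3 men, size.** Counting whole cycles, (26 − 12) × 28 = 392 days, and then adding about 2 months for the different tails overstates the gap. Lenalidomide stops on Day 21 and rituximab on Day 1, so the last doses are 701 − 329 = 372 days apart, and 372 − 28 + 91 = 435.
- **Part 3 men, source.** A reader might blame the unexplained *or* in Section 3.7.6 for the whole gap. That sentence also requires condoms during treatment, and a man on rituximab maintenance is still being treated. The long gap lies between criterion 10 and Section 3.7.6.
- **Harm.** The consent pages are not in the reviewed text, so what subjects were actually told cannot be judged.

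The reply does not remove the conflict over Part 3 men. Criterion 10 and Section 3.7.6 give different end dates, and nothing in the protocol decides between them.

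**Conclusion.** The inconsistencies are in the current protocol text and should be reconciled, but they carry unequal weight.

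The main live item is condom use by Part 3 men: about day 357 under criterion 10 against about day 792 under the rituximab limb of Section 3.7.6. The gap of about 435 days is the maximum between those two limbs on planned dosing. It assumes full lenalidomide and rituximab treatment, no delays, and 91 days for 3 months. If treatment in Section 3.7.6 also means acalabrutinib, which continues to progression, the schedule gives no end date for that reading.

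The Part 1 mismatch of 3 against 12 months is real but is now mainly a consistency correction. The Part 3 start times differ by 14 to 28 days and can be satisfied together, so they need alignment rather than a choice between incompatible rules.

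A reader might also infer that Section 6.3.4 is in conflict. Its pregnancy reporting window already matches Section 3.7.6 for women. The 3-month sperm-donation rule for men is a separate requirement, stated consistently, and is not part of the problem.

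The documents do not give Part 3 dosing dates, so whether any subject is still inside an affected window has to be checked. No view is taken on which duration, start or governing limb is right.

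**What to change.** The sponsor should:

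1. Reconcile the synopsis and Sections 3.4.1, 3.4.5 and 3.7.6 to one stated window per drug and sex.
2. State which limb governs the end of condom use for men, and whether treatment in that sentence includes acalabrutinib.
3. Align the Part 3 start of contraception in Section 3.7.6 with criterion 9b, or cross-refer to it.
4. Check Section 6.3.4 against the reconciled windows.
5. Check dosing records, and inform any subject found to be still inside an affected window.

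The choice of windows belongs to the sponsor and its clinical and safety advisers. The cost is protocol wording, a matching check of the consent wording, and a short review of last-dose dates. The SAP and the analyses do not change.
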